Allocation and Randomization: Treatment allocation will be done using a random, computer generated table, with an allocation ratio of 1:1, using random permuted block sizes. Stratification based on each centre (3 sites). These syringes (4*10 mls)-in sealed packages, labelled with serial numbers and no identifiers for the medication, shall be deposited in a safe drug locker, within the fridge, at the respective PACU. The actual randomization, for each patient happens as they enter into the PACU after surgery. The PACU nurse allotted for that patient will obtain the next medication package in series to be used for that patient. To ensure that the respective patient and medication is matched for subsequent analysis, the nurse will attach the medication sequence number on the patient study records, with no identifiers of actual drug. The PACU nurse shall also note down the patient hospital ID on the medication syringe, once it is taken out, to ensure there is no mix up.

Blinding: The study allocation will be blinded to patients, treating nurses, physicians, research assistant and investigators. The allocation order will be available only to the person responsible for randomizing and the pharmacists involved in the study at each centre.

Application of Intervention:

The Operating Room Protocol: Patients included in the study need to be managed according the OR protocol provided in Appendix 2. In brief, the patient will only have a GA, with local infiltration provided at the end of the surgery. Long acting opioid medications (morphine and hydromorphone) are not administered in the OR. LA infiltration is done within a range of 20-30 mls (based on laparoscopic or open surgeries) using 0.25% bupivacaine with or without adrenaline.

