PACU Stay: The actual study intervention (hence randomization) will only become applicable once the patient is moved to the PACU. Every patient will be treated as per the protocol during the intraoperative management, which primarily restricts the use of any study opioids. The details are provided in appendix 2. The nurse looking after the study patient in PACU will administer the medication as per the study protocol. This would include analgesia with equipotent doses of M or HM administered in titrated doses. Syringes will be pre-prepared from the pharmacy in EMUs; 1ml=1mg of morphine or 0.2 mg of hydromorphone. We shall consider a potency ratio of 1:5 (M: HM), considered equivalent in literature.⁽⁹⁾ Analgesia will be provided according to the following guideline. A similar method has been advised to be safe and effective for titrated analgesia in PACU.⁽²⁴⁾ Readiness to discharge from PACU and outcomes are noted at 2 hrs, or at the time of discharge to DSU.

Most Effective Opioid Analgesia in Ambulatory Surgeries: a randomized control, investigator blinded, parallel group with superiority design study of Morphine versus Hydromorphone
[name], Principal Investigator SJHH
[name], Principal Investigator HHS

PACU Protocol (titrate the opioid medication to achieve desired pain score)

- Patient to be asked for their pain score, and if it is more than 4 out of 10 (NAS): to receive the 1st dose within 5 minutes after coming to PACU: 0.04mg/kg morphine units (rounding off to the nearest 1 ml or 0.5 ml); with a maximum of 3 mg of morphine equivalents.
- Repeat doses: 0.02 mg/kg morphine units every 5-10 minutes to titrate for analgesia and side effects (rounding off to the nearest 1 ml or 0.5 ml)
- If no side effects observed-titrate to have analgesia: NAS =<4/10.
- If Nausea-Vomiting observed: record it in the CRF provided and treat it with antiemetics (Ondansetron 1-4 mg IV, Dimenhydrinate 25-50 mg)
- If patient is too sedated (<3-Ramsey Sedation Scale)-withhold the next dose and restart the bolus if the score is >3
- If respiratory depression present, withhold the next dose, treat with Naloxone if necessary.
- Ketorolac IV 15-30 mg as rescue medication if patient does not tolerate the study opioid or if the patient does not satisfy the success of satisfactory analgesia at more than 1 hr.

DSU Stay and Protocol:

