OUTCOME MEASURE	TYPE	MEASUREMENT	TIME OF MEASUREMENT	ANALYSIS METHOD
Primary outcome Satisfactory Analgesia with minimal PONV	Binary	NAS=<4/10 VDS<2/5	At 2hrs or at the time of discharge from PACU	Chi-square
Severe Itching	Binary	VAS>5/10	At 2hrs or at the time of discharge from PACU	Chi-square or Fisher's test (as appropriate)
Severe Sedation	Binary	Ramsey Score >3/6	At 2hrs or at the time of discharge from PACU	Chi-Square or Fisher's test (as appropriate)
Severe Respiratory Depression	Count	All cases needing treatment as counts	At 2hrs or at the time of discharge from PACU	Chi-square or Fisher's test (as appropriate)
Use of Ketorolac	Continuous	Total dose used per patients as a rescue therapy	At 2hrs or at the time of discharge from PACU	T test
Mean dose of Analgesic Used	Continuous	Dose of Analgesic used per patient in EMU	At the time of hospital discharge	T test

Most Effective Opioid Analgesia in Ambulatory Surgeries: a randomized control, investigator blinded, parallel group with superiority design study of Morphine versus Hydromorphone
 [name], Principal Investigator SJHH
 [name], Principal Investigator HHS

Patient Satisfaction-Mean score (0-10)	Continuous	Mean Score calculated between 0 to 5 scale	At the time of hospital discharge	T test
Time to discharge from PACU	Continuous	Mean time in hrs	At 2hrs or at the time of discharge from PACU	T test
Time to discharge from the hospital	Continuous	Mean time in hrs	At the time of hospital discharge	T test

Outcomes at Post-operative Day 1:

Patients will be approached by 1-2 phone calls shall be done during the next day; if unanswered, a repeat call will be made on the subsequent day (2nd day after discharge); for responders, the following questions will be asked.

1. What was your average pain score over the last 24 hrs, in 0-10 NAS scale, after you were discharged home?
2. After discharge, did you have nausea-severe enough to require medications at home?
3. After discharge, did you have vomiting-severe enough to require medications at home?
4. After discharged home, did you require a visit to ER, or readmission?

Outcomes at 3 months:

Patients will be contacted by a mailed package at 3 months after surgery to collect the following outcomes.

1	Do you have Persistent Pain (which started with or after surgery), at or near the surgical area?	Yes or No
2	Intensity of Pain	NAS: 0-10
3	Brief Pain Inventory-Interference Items 7 Items: each item scored between 0-10	

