4	Global Impression of Change	Likert scale 1-7

Most Effective Opioid Analgesia in Ambulatory Surgeries: a randomized control, investigator blinded, parallel group with superiority design study of Morphine versus Hydromorphone
[name], Principal Investigator SJHH
[name], Principal Investigator HHS

5	Analgesic Use: Did you have to use any pain medications for more than 1 month, to help with pain, which started with or after Surgery?	Yes or No
---	---	-----------

Statistical Analysis: The study will be analyzed using an intention to treat approach. The individual outcomes along with their respective analyses method have been listed within the table 1. Broadly the dichotomous outcomes will be reported as proportions and analyzed using a chi-square test to detect a significant difference ($p<0.05$). Precision will be reported using 95% CI. Continuous outcomes will be analyzed using an unpaired 2-tailed student t test for significance ($p<0.05$). Means and standard deviations shall be reported along with 95% CI. We also plan to perform logistic multivariable regression analysis to account for the influence of baseline covariates, which are listed in appendix 1. A sensitivity analysis will be performed to compare the effects of laparoscopic surgeries vs open surgeries.

Trial Management: This trial will be conducted at 3 hospital sites affiliated with McMaster University, Hamilton: St Joseph's Hospital, McMaster University Hospital and Juravinski Hospital.

Data Management and Quality Control: All study data including CRFs of each patient, shall be securely stored at the central office. A summary table indicating study timeline from enrollment to final follow-up (<http://www.spirit-statement.org/title/>) shall be included for each patient.⁽²⁷⁾ CRF's will be collected as paper forms. They shall be periodically cross-checked for completeness and entered into a suitable electronic master file. All reports of incorrect randomizations, protocol violations or incomplete data shall be noted.

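### The pain score taken before the first study dose enters no pre-specified analysis, which gives up precision, mainly on the opioid-dose comparison

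*Combined protocol and SAP*

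**What the plan says.** The PACU Protocol opens with this step: "Patient to be asked for their pain score, and if it is more than 4 out of 10 (NAS): to receive the 1st dose". Titration then aims at a score of 4 or less. Under Allocation and Randomization, "The actual randomization, for each patient happens as they enter into the PACU after surgery", and under Blinding, "The study allocation will be blinded to patients, treating nurses, physicians, research assistant and investigators". The score is therefore taken before study drug, by staff who do not know the allocation.

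The first secondary objective is the amount of analgesic consumed in the PACU, in morphine equivalents. Table 1 defines the matching outcome as "Dose of Analgesic used per patient in EMU", timed at hospital discharge, and assigns it a t test. The Statistical Analysis section confirms this: "Continuous outcomes will be analyzed using an unpaired 2-tailed student t test for significance". The only adjusted analysis is in the same section: "We also plan to perform logistic multivariable regression analysis to account for the influence of baseline covariates, which are listed in appendix 1".

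Appendix 1, as shown, lists demographics, Apfel score, anxiety and depression, pain catastrophizing, preoperative pain at the surgical site, chronic pain elsewhere, and surgical and anaesthetic details. It lists no pain score on PACU arrival. The NAS in the primary outcome is the one recorded at 2 hours or PACU discharge.

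**The concern.** The score is tied to the dose by the protocol itself. A patient arriving at 4 or below triggers no first dose and already meets the pain half of SAME. A patient arriving at 9 must be brought down five points. Treatment cannot influence the score, so it is a legitimate covariate and plausibly a useful one.

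The unadjusted t test leaves all the variation in dose that arrives with the patient in the error term. The planned adjusted model does not help: it is logistic, so it cannot cover a continuous dose, and its covariate list omits the score. If the arms differ by chance in arrival pain, a reader will ask whether that explains a dose difference, and the plan has no pre-specified answer. An adjustment chosen after the data are seen would be less convincing.

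**Working it through.** **1. The plan's own figure.** Inputs from Sample Size Calculation: 80% vs 90%, two-sided alpha 0.05, power 90%. With pooled variance under the null and no continuity correction:

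n = [1.96·√(2·0.85·0.15) + 1.2816·√(0.8·0.2 + 0.9·0.1)]² / 0.10² = (0.990 + 0.641)² / 0.01 ≈ 266 per group.

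This matches the stated 266. At the target of 275 per group, power is 90.9%. The sample size does not depend on the point raised here.

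**2. Dose: relative gain.** Adjusting for a covariate with correlation r to the outcome multiplies the residual variance by 1 − r². A comparison with 80% power unadjusted has a standardised effect of 1.96 + 0.84 = 2.80, so adjusted power = Φ(2.80/√(1 − r²) − 1.96). Equivalent size = 275/(1 − r²). The documents do not give r, so a range is shown.

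| assumed r | variance factor | adjusted power | equivalent n per arm |
|---|---|---|---|
| 0.3 | 0.91 | 83.6% | 302 |
| 0.5 | 0.75 | 89.9% | 367 |
| 0.7 | 0.51 | 97.5% | 539 |

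**3. Dose: illustrative scale.** Risk Assessment and Protocol Adherence cites a mean titrated dose of 0.17 mg/kg with SD 0.10 mg/kg. Table 1 measures dose per patient, not per kg, so these absolute figures are only illustrative; the ratios in step 2 do not depend on the unit.

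- Unadjusted 95% CI half-width: 1.96·0.10·√(2/275) = 0.0167 mg/kg.
- Adjusted, multiplying by √(1 − r²): 0.0159, 0.0145 and 0.0119 mg/kg at r = 0.3, 0.5 and 0.7.

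**4. Chance imbalance.** An imbalance of 1.96 standard errors in the score is 1.96·√(2/275) = 0.167 SD. It would shift the dose difference by r·0.10·0.167, that is 0.005, 0.008 and 0.012 mg/kg at r = 0.3, 0.5 and 0.7. Each is smaller than the unadjusted half-width of 0.0167.

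**5. SAME.** In a simulation with 275 per arm and marginal rates fixed at 80% and 90% (2,000 trials per setting), the chi-square test was compared with a logistic model containing arm and a standardised pain covariate. The covariate strength is assumed.

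| log-odds per SD | chi-square power | adjusted power |
|---|---|---|
| 0 | 90.9% | 90.6% |
| 0.5 | 91.3% | 92.0% |
| 1.0 | 91.0% | 93.8% |

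Each power has a Monte Carlo standard error of about √(0.91·0.09/2000) = 0.6 points. The gain is about 1 to 3 points where the score is predictive. The comparator is the plain chi-square test; the increment over the planned model with Appendix 1 covariates was not computed.

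**The case against.** The strongest reply is that this is about efficiency, not error. That stands. Under randomization the t test and chi-square test are valid, chance imbalance is already reflected in their p values and intervals, and the larger gains fall on a secondary outcome with no stated power target.

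The size of the gain is also assumed, and r could be modest. The first bolus depends on whether the score exceeds 4, not on how far; it is weight-based and capped. Later boluses may be withheld for sedation or respiratory depression. For SAME, titrating to the target weakens the link between arrival and final pain, and half of the composite is PONV. Appendix 1 already supplies preoperative pain, catastrophizing, anxiety, Apfel score, surgical approach and intraoperative opioids, several of which may predict arrival pain. These points stand as reasons to show a range and to promise little on SAME.

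A reader might infer that the score goes unrecorded, so that no adjustment is possible. The documents do not support this. The PACU record form is not reproduced, and the Appendix 1 forms as shown also lack fields for 2-hour NAS, PONV score, study-drug dose and ketorolac, all of which Table 1 requires. What can be said is that no adjustment is pre-specified.

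Two practical objections affect the remedy. Appendix 1 has an item for cases where PACU is on hold and the OR anaesthesiologist starts the protocol, so a score on PACU arrival could follow the first study dose. And the objective confines dose to the PACU, whereas Table 1 times it at hospital discharge; counting oral opioids given in the DSU could dilute the correlation. Neither removes the point.

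**Conclusion.** The point holds as a recommended improvement. A blinded, pre-treatment pain score that triggers dosing is asked of every patient and appears in no pre-specified analysis. The cost is precision on dose: a variance 9% larger than necessary relative to the unadjusted total if r = 0.3, and 25% if r = 0.5, with r an assumption throughout. On SAME the gain is at most about 1 to 3 power points over the chi-square test, and possibly less over the planned adjusted model.

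It would be wrong to conclude that the planned tests are biased or that the trial is too small: randomization protects the tests, and the stated sample size reproduces exactly. The dose figures rest on a linear relation between score and dose and are approximate if many patients receive none.

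**What to change.** 1. Confirm that the PACU form has, or add, a field for the last NAS before the first study dose, wherever that dose is given. For patients who never receive study drug, use the PACU arrival score.
2. Reconcile the dose window between Specific Objectives (PACU) and Table 1 (hospital discharge), and define the outcome for this analysis as PACU opioid dose in EMU.
3. Pre-specify a linear model for that dose with arm, pre-dose NAS and weight (boluses are set per kg), with robust standard errors because some doses may be zero.
4. Add pre-dose NAS to the planned logistic model for SAME. The chi-square test can stay as the primary analysis.
5. Report adjusted differences with 95% CIs beside the unadjusted results.

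The cost is at most one form field, for a score the nurse already asks, and a little extra analysis. No patient's treatment changes.

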Hence, we will also look for any differences in pain, nausea and vomiting over the first 24 hrs after the surgery, along with chances of readmission or ER visits within the same period, post discharge. At 3 months, we will look for the incidence of persisting pain after surgery.

Hypothesis

In patients who undergo ambulatory surgical procedures causing at least moderate pain, hydromorphone (HM) increases the proportion of patients who would demonstrate 'satisfactory analgesia [$=<4/10$ NAS] with minimal or no postoperative nausea-vomiting (PONV) [$<2/5$ VDS] as compared to morphine (M), when both are administered intravenously, in equianalgesic doses, and are compared at 2 hours after surgery in PACU.

2. Specific Objectives

The primary objective of this study is to compare the proportion of patients with SAME (satisfactory analgesia and minimal emesis) after AS, when using M compared with HM, during the immediate postoperative hospital stay.

Secondary objectives include:

1. Total dose of analgesic used in PACU, in morphine equivalents,
2. Time to discharge or readiness to discharge from the DSU,
3. Proportion of pain, and its comparison after discharge, within 24 hours,
4. Proportion of nausea, and its comparison after discharge, within 24 hours,
5. Proportion of vomiting, and its comparison after discharge, within 24 hours,
6. Incidence of CPSP at 3 months after discharge

The tertiary objectives include:

1. Proportion of patients with severe itching,

Protocol Version Date: Version 5 / June 23, 2015

Most Effective Opioid Analgesia in Ambulatory Surgeries: a randomized control, investigator blinded, parallel group with superiority design study of Morphine versus Hydromorphone

[name], Principal Investigator SJHH

[name], Principal Investigator HHS

2. Proportion of patients with significant sedation,
3. Proportion of patients with significant respiratory depression,
4. Patient satisfaction score at the time of discharge,
5. Time to discharge or readiness to discharge from the PACU,
6. Use of ketorolac as a rescue medication,

METHODS

The study is designed as a multisite, 2 arm, parallel, superiority design with randomization of patients and blinding of patients, health care providers (physicians and nurses) and research personnel (research coordinator and data analyst). Patients will be stratified based on site and laparoscopic/open surgeries. Intention to treat approach will be used for design and analysis.

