Risk Assessment and Protocol Adherence: This trial does not entail any higher risk than the standard of care to the patients. This is a pragmatic trial and involves the use of medications of known benefit and in clinically acceptable doses. It also involves using only short acting opioids in the form of fentanyl or sufentanil or remifentanil in small boluses or infusion. Although for some this might differ from their normal practice, we do not anticipate this to be a major issue as the surgeries would be of 1-2 hrs duration and can be effectively and safely managed with short acting opioids until patients are shifted to PACU. Protocol also involves the use of study medications in PACU at an initial dose of 0.05mg/kg, followed by 0.03/mg/kg EMU boluses. Studies have shown that IV Morphine titration in PACU, after moderately painful surgeries

Most Effective Opioid Analgesia in Ambulatory Surgeries: a randomized control, investigator blinded, parallel group with superiority design study of Morphine versus Hydromorphone

[name], Principal Investigator SJHH

[name], Principal Investigator HHS

require a mean morphine dose of $0.17 +/ - 0.10$ mg/kg.^(17,28) Only doses as high as 0.15mg/kg were found to be associated with significant adverse effects.⁽²⁹⁾

Potential Pitfalls (Study Limitations): Despite being a randomized study, there exists the possibility of bias due to unequal distribution of unknown covariates. The primary outcome of SAME is being measured using subjective pain scale of NAS and VDS for emesis. Although there are inherent limitations of such scales, we think they are widely used in practice and are well validated. We have considered a potency ratio of 1: 5 (M: HM) as it is commonly used and supported by the literature. However, we do accept that there is a much wider range described in some studies.

STUDY SIGNIFICANCE:

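### Total opioid dose, the first-listed secondary outcome, is compared without adjustment for body weight, although boluses are set largely by weight and weight is recorded: a possible modest loss of precision, not bias

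*Combined protocol and SAP*

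**What the plan says.** Specific Objectives lists as secondary objective 1: "Total dose of analgesic used in PACU, in morphine equivalents". Table 1 gives the measurement as "Dose of Analgesic used per patient in EMU", a continuous outcome with a t test. The Statistical Analysis section confirms the method: "Continuous outcomes will be analyzed using an unpaired 2-tailed student t test for significance ($p<0.05". The only covariate adjustment described there is a multivariable logistic regression on the Appendix 1 baseline variables. Weight is among those variables (demographics, item 5), but it is not a stratification factor.

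Under the PACU Protocol the first dose, given when the pain score exceeds 4, is "0.04mg/kg morphine units (rounding off to the nearest 1 ml or 0.5 ml"), "with a maximum of 3 mg of morphine equivalents". Later boluses follow this rule: "Repeat doses: 0.02 mg/kg morphine units every 5-10 minutes to titrate for analgesia and side effects". They are rounded too, and no cap is stated for them. The end point of dosing is effect: "If no side effects observed-titrate to have analgesia: NAS =<4/10". Risk Assessment and Protocol Adherence says that earlier studies of titration in PACU "require a mean morphine dose of" 0.17 +/- 0.10 mg/kg.

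**The concern.** When bolus size depends on weight, a heavier patient who gets the same number of boluses receives more drug. Differences in weight between patients may then add to the spread of total EMU while carrying no information about morphine versus hydromorphone. An unadjusted t test leaves that spread in the standard error. Weight is measured before treatment and is already collected, but the plan has no analysis that uses it for this outcome, because logistic regression needs a binary response. At stake is some precision on the first-listed secondary outcome, with a correspondingly wider confidence interval for any opioid-sparing effect.

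**Working it through.** **The plan's own figure.** The documents give no sample size or power for the dose outcome. The primary-outcome figure reproduces: n = [1.960·√(2·0.85·0.15) + 1.282·√(0.8·0.2 + 0.9·0.1)]² / 0.10² = 265.9, so 266 per group. The check below uses the recruitment target of 275 per group.

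**Inputs.** Titrated dose 0.17 +/- 0.10 mg/kg (Risk Assessment and Protocol Adherence), so CV_r = 0.10/0.17 = 0.588 and CV_r² = 0.346. The documents give no weight distribution. Assumption: weight CV of 15-22%; for absolute figures, 80 +/- 15 kg (CV 0.1875).

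**Case A: need scales with weight.** Let total = r × w, with r the mg/kg dose, w the weight, and the two independent. Then CV_total² = CV_r² + CV_w² + CV_r²·CV_w², and the share of variance explained by a linear term in weight is R² = CV_w² / CV_total².

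| CV_w | CV_total² | R² | 275 × (1 − R²) |
|---|---|---|---|
| 0.15 | 0.346 + 0.0225 + 0.0078 = 0.376 | 6.0% | 259 |
| 0.1875 | 0.346 + 0.0352 + 0.0122 = 0.393 | 8.9% | 250 |
| 0.22 | 0.346 + 0.0484 + 0.0167 = 0.411 | 11.8% | 243 |

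The last column is the size per group at which the adjusted analysis would match the unadjusted test on 275.

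Power of the unadjusted test at a difference that the adjusted analysis detects with 90% power is Φ(3.242·√(1 − R²) − 1.960). This is 0.88 at R² = 6.0% and 0.86 at 11.8%, a loss of 2 to 4 points.

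At 80 +/- 15 kg the mean dose is 80 × 0.17 = 13.6 mg. The raw SD is 13.6 × √0.393 = 8.53 mg, and the SD after adjustment is 0.10 × √(80² + 15²) = 8.14 mg. Multiplying by √(2/275) = 0.0853 gives standard errors of 0.73 and 0.69 mg. The difference detectable with 90% power is 3.242 × SE: 2.36 mg unadjusted, 2.25 mg adjusted.

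**Case B: some patients receive no dose.** The first dose is conditional on a pain score above 4. Read 0.17 +/- 0.10 as applying to those dosed, and let a fraction p₀ receive none, independently of weight. Then CV_r² becomes (1 + 0.346)/(1 − p₀) − 1, which is 0.683 at p₀ = 20% and 0.923 at 30% (both assumed). R² over the same weight CVs is 3.1-6.3% and 2.3-4.8%.

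**Case C: need scales less than proportionally, or not at all.** Titration was simulated with the 3 mg cap, 0.5 ml rounding and 0.02 mg/kg repeats, at assumed weights of 75 +/- 12, 80 +/- 15 and 80 +/- 20 kg (CV 16-25%).

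| Need in mg | R² of weight | Relative variance, EMU/kg over EMU |
|---|---|---|
| proportional to weight | 0.07-0.15 | 0.81-0.90 |
| proportional to √weight | 0.02-0.05 | about 1.00 |
| unrelated to weight | about 0 | 1.12-1.27 |

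The first row shows that Case A survives the cap and rounding. The last shows that dividing by weight can add noise.

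**Validity.** With need proportional to weight at 80 +/- 15 kg and no treatment effect, the unadjusted t test rejected in 5.05% of 4,000 simulated trials.

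**The case against.** The strongest objection is that dosing is titrated to effect. A lighter patient with smaller boluses may simply need more of them, so the total in mg need not follow weight. A mean and SD in mg/kg do not show how need scales. This stands: the 6-12% is conditional, not a property of the trial. Part of it can be answered. Where sedation, ketorolac rescue or the 2-hour limit ends titration early, total dose is boluses received times bolus size, which follows weight even if need does not. The documents do not say how often that happens.

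Three stronger readings are tempting, and the documents do not support them.

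- *Every bolus is proportional to weight.* A reader might infer this from the per-kg figures. But the first bolus is capped at 3 mg, reached at 3/0.04 = 75 kg, and doses are rounded. With 0.5 ml rounding, everyone between 68.75 and 87.5 kg gets the same sequence: 3 mg, then 1.5 mg per repeat.
- *A chance imbalance in weight would bias the comparison.* At SD 15 kg, an imbalance at the 95% limit is 1.96 × 15 × 0.0853 = 2.5 kg, which moves the dose difference by 2.5 × 0.17 = 0.43 mg, about 0.6 of the 0.73 mg standard error. That standard error already contains this variation.
- *The outcome should become EMU per kg.* This changes the stated objective, for which total drug used is a legitimate quantity. By Case C it loses precision when need in mg is unrelated to weight.

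It can also be said that this is routine advice on a secondary outcome. That is fair, and it limits the weight of the point.

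**Conclusion.** The point holds as a minor improvement. The dose outcome is analysed without a recorded baseline variable that helps set bolus size, and the planned logistic model cannot supply the adjustment. The planned test is valid and unbiased. The possible loss is about 6-12% of the variance, or 2 to 4 points of power, if need scales with weight; less if some patients receive no dose or need scales less than proportionally; and about nothing if need in mg is unrelated to weight. These sizes rest on the protocol's 0.17 +/- 0.10 mg/kg applying to this population and on an assumed weight CV of 15-22%. Covariate adjustment is preferable because it gains if weight matters and costs almost nothing if it does not. The primary outcome and its sample size are untouched.

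**What to change.** In Table 1, keep total EMU per patient as the outcome and replace the t test by a linear regression of EMU on arm with baseline weight as a prespecified covariate. Report the adjusted difference with its 95% CI, and show raw means and SDs by arm as description. List EMU per kg, if wanted, only as a supportive analysis. State in Statistical Analysis that continuous outcomes may be covariate-adjusted by linear regression. Settle the wording before unblinding, so that raw, adjusted and per-kg results are not open to selection.

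The cost is SAP wording: no new data, patients or change in conduct.

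Two passages should be reconciled at the same time. The dose is counted in PACU under Specific Objectives but at hospital discharge in Table 1, which could bring in the oral analgesics given in the DSU. The per-kg bolus sizes also differ between the PACU Protocol (0.04 then 0.02 mg/kg) and Risk Assessment and Protocol Adherence (0.05 then 0.03 mg/kg). Neither changes the recommendation.

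### Patients reached on day 2 are asked the day-1 questions, so their answers do not match the 24-hour window of secondary objectives 3 to 5

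*Combined protocol and SAP*

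**What the plan says.** Three secondary objectives (Specific Objectives, items 3 to 5) set the window:

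- "Proportion of pain, and its comparison after discharge, within 24 hours"
- "Proportion of nausea, and its comparison after discharge, within 24 hours"
- "Proportion of vomiting, and its comparison after discharge, within 24 hours"

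The rationale just before the Hypothesis starts the clock elsewhere. It speaks of "any differences in pain, nausea and vomiting over the first 24 hrs after the surgery", together with "chances of readmission or ER visits within the same period, post discharge".

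Under Outcomes at Post-operative Day 1, and again in the 24-hour part of Appendix 1, one or two calls are made on the next day; "if unanswered, a repeat call will be made on the subsequent day (2nd day after discharge". Four questions follow, the same on either day:

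- Pain: "What was your average pain score over the last 24 hrs, in 0-10 NAS scale, after you were discharged home"
- Nausea: "After discharge, did you have nausea-severe enough to require medications at home"
- Vomiting: worded like the nausea question.
- ER visit or readmission: any such event since going home.

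The Study Significance section presents the first-day incidence of pain, nausea and vomiting as a result that the trial will deliver for planning health services.

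**The concern.** The objectives fix a 24-hour period, but the questions do not. The pain question counts back from the call, so its window moves with the day of the call. The other three run from discharge to the call, so their window lengthens with it. Day-1 and day-2 answers would then be pooled as one outcome although they describe different periods.

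The documents give no separate wording for a day-2 call, no instruction to limit answers to the first day, no onset times and no analysis rule for late answers. The 24-hour section of the case record form lists no field for the date or time of the call, so as written it does not let the analyst identify late responders. At stake are the first-day incidence figures and, under further conditions, the comparison of arms on three secondary outcomes and on ER/readmission.

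**Working it through.** **The plan's own figure.** The documents give no figure for the 24-hour outcomes. The only sample size is for the primary outcome: 80% vs 90%, two-sided alpha 0.05, power 90%. With pooled variance and no continuity correction, n = [1.960 × √(2 × 0.85 × 0.15) + 1.282 × √(0.80 × 0.20 + 0.90 × 0.10)]² / 0.10² ≈ 266 per group. This matches the protocol and does not depend on the present point.

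**Windows, with assumed clock times.** The documents give neither discharge times nor call times. Assume discharge at 12:00, 15:00 or 18:00 and calls at 09:00, 13:00, 17:00 or 20:00, which makes 12 combinations per day.

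- Hours from discharge to call: t = 24 × day + call hour − discharge hour.
- Literal pain window: from max(0, t − 24) to t.
- Overlap with the first 24 hours: min(24, t) − max(0, t − 24), or 0 if negative.
- Window of the other three questions: 0 to t.

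| | Day-1 call | Day-2 call |
|---|---|---|
| Hours since discharge (t) | 15 to 32 | 39 to 56 |
| Pain window, overlap with first 24 h | 15 to 23 h | 0 to 9 h (none in 6 of 12) |
| Other questions, hours beyond 24 | 0 to 8 | 15 to 32 |

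The earliest day-2 case (discharge 18:00, call 09:00) has t = 48 + 9 − 18 = 39. The pain window is hours 15 to 39 and shares 24 − 15 = 9 hours with the first day. The latest (discharge 12:00, call 20:00) has t = 56. The window is hours 32 to 56 and shares none.

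Day-1 calls are not exact either. In 6 of the 12 combinations t is below 24 (15, 18, 19, 21, 22 and 23 hours), so the first 24 hours are not yet over.

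**What this could do to results.** Every input below is an assumption; the documents supply none. Let s be the share reached on day 2, taken as 0.2 to 0.4.

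- *Incidence of nausea, vomiting, ER/readmission:* overstatement = s × e, where e is the share of late responders whose only events fall after 24 hours. With e = 0.05 to 0.10, this is 0.2 × 0.05 = 0.01 to 0.4 × 0.10 = 0.04, or 1 to 4 percentage points.
- *Mean pain over both arms:* shift = s × fall in NAS from day 1 to day 2. With a fall of 1 to 2 points, this is 0.2 × 1 = 0.2 to 0.4 × 2 = 0.8 points too low.
- *Difference between arms in mean pain:* bias ≈ (difference in s between arms) × fall. With a difference of 0.05 to 0.10, this is 0.05 × 1 = 0.05 to 0.10 × 2 = 0.2 points. With equal timing it is zero.

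**The case against.** The strongest reply is that the script is identical in both arms and that patients, nurses, physicians, the research assistant and investigators are blinded. A shift common to both arms largely cancels from the difference, and nothing in the documents shows that a PACU opioid changes who answers the telephone next day. This stands. A reader might take the 0.2 to 0.8 point shift as bias between arms; the documents do not support that. It is a shift in the overall mean built on assumed inputs. It also does not size the stated endpoint, because objective 3 is a proportion. Cancellation does not protect the incidence estimates, however. And if a true effect on pain were confined to the first day (an assumption), late answers would dilute it by about the day-2 share even with equal timing.

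A reader might also infer that late responders fail to report the first 24 hours on every question. That is not so. The nausea, vomiting and ER/readmission questions reach back to discharge and so include that period. Only the pain question, read literally, loses it.

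Even the pain question can be defended. Its last words point to the time at home, and the form places it under a 24-hour heading, so a caller could take it as the first day. That makes it ambiguous rather than plainly wrong. On day 2, though, a patient may answer for the past day or for all the time since discharge, and neither is the objective's window.

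It is also tempting to say that late answers cover up to 48 hours, or at most twice the intended period. With no call times given, neither is a limit; the illustration reaches 56 hours.

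Finally, the Data Management section plans a per-patient timeline from enrolment to last follow-up. It may hold contact dates, but it does not promise call times.

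**Conclusion.** The mismatch is real, and nothing in the documents resolves it. For patients first reached on day 2, the literal pain question misses most or all of the first 24 hours (0 to 9 hours shared under the assumed clock times). The other three questions include that period but are not confined to it, so with accurate recall their proportions can only be too high.

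The main consequence is for the first-day incidence figures. A false difference between arms arises only if response timing differs by arm, which the documents neither suggest nor exclude. The size of either effect cannot be computed, because the share reached on day 2 is not stated; the percentages and points shown are illustrations. The affected outcomes are secondary objectives 3 to 5, plus ER/readmission, which the rationale names but the list of objectives does not. The primary outcome and the sample size are untouched. The point should be corrected, but it does not threaten the trial's main conclusion.

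**What to change.** 1. Settle time zero. The rationale, Study Significance and the form's 24-hour label count from surgery; objectives 3 to 5 and the four questions refer to discharge. Use one origin throughout.
2. Anchor all four questions to the first 24 hours from that origin, whichever day the call is made. If the call comes before 24 hours have passed, ask about the time from the origin up to the call.
3. Record the date and time of the call on the 24-hour form, so that late and early calls can be identified.
4. Add to Statistical Analysis a sensitivity analysis of the 24-hour outcomes that excludes day-2 responders, and report the share reached on day 2 by arm.

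The cost is new script wording, one extra form field, one additional analysis and slightly longer recall for late responders.
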